The Indego exoskeleton was approved for use by the FDA in February of 2016 with individuals with spinal cord injury (SCI) at levels T4 and below for rehabilitation use, and for T7 and below for personal use in the home and community. Shepherd Center was instrumental in leading the multi-site clinical trials that led to the Indego FDA approval for persons with SCI.

Shepherd Center, in collaboration with Vanderbilt University and Parker Hannifin Corporation, has also led the clinical research efforts for use of Indego for persons with hemiparesis resulting from cerebrovascular accident (CVA) since 2012.

A publication from our earliest work using Indego with persons with CVA (Shepherd RRC project #510) can be found here: S. A. Murray, K. H. Ha, C. Hartigan, and M. Goldfarb, "An assistive control approach for a lower-limb exoskeleton to facilitate recovery of walking following stroke," Neural Systems and Rehabilitation Engineering, IEEE Transactions on, vol. 23, pp. 441-449, 2015. Shepherd Center Principal Investigator was [name] [name]

A second manuscript from an Indego trial for persons with CVA conducted in 2015 and 2016 as a collaborative effort between Shepherd Center, Vanderbilt University and Parker Hannifin Corporation (Shepherd RRC Project #660) has been submitted but not yet accepted for publication. A full copy of the manuscript is attached in this IRB submission: Spencer A. Murray, Student Member, IEEE, Clare Hartigan, Casey Kandilakis, Elizabeth Sasso, and Michael Goldfarb, Member, IEEE "A Preliminary Crossover Study of Exoskeleton Control Methodologies for Gait Rehabilitation Post-Stroke". Shepherd Center Principal Investigator was [name] [name]

The Indego User Manual is attached in this submission. In addition, videos and other Indego information can be found at www.Indego.com

STUDY SYNOPSIS**Primary Objective:**

- To demonstrate that the Indego® device is safe to use as a gait training intervention for persons with hemiplegia due to CVA.

Results of this multi-site study to include 40 subjects will be submitted to the FDA as part of a 510K Parker Hannifin submission to seek FDA approval for Indego use with persons following stroke.

Hypothesis:

- Indego can be safely used as a gait training intervention for persons with hemiplegia due to CVA for persons with mild, moderate or severe stroke.

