- Indego can be safely used as a gait training intervention for persons with hemiplegia due to CVA for persons with acute (less than 2months), sub- acute (2-6 months) and chronic (greater than 6 months) onset.
- Following six Indego sessions, persons with hemiplegia due to CVA may show improvements in mobility when comparing pre- training measurements to post-training measurements.

Study Design:

Forty subjects in total will be enrolled across nine clinical sites: Shepherd Center (GA), Cedar Sinai Medical Center (CA), Rusk Rehabilitation (NY), Sheltering Arms (VA), St Charles Hospital (NY), Craig Hospital (CO), Kessler Foundation (NJ), Rehabilitation Institute of Chicago (Shirley Ryan AbilityLab, IL) and TIRR Memorial Hermann (TX). Subjects will be seen three times per week for two weeks.

Up to five subjects are expected to be enrolled at Shepherd Center.

	Session Content	Session Duration
Session 1	Consent Initial Evaluation and Fit	2 hours
Session 2	Indego Training Sessions	1 hour
Session 3		
Session 4		
Session 5		
Session 6	Indego Training Session Final Evaluation	2 hours

Study duration for each individual enrolled is two weeks. If a session is missed, attempts must be made to reschedule within the same week. The maximum amount of time the protocol may be interrupted or extended (due to illness, weather, other) is two weeks. The number of study visits remains the same.

Shepherd Center will be provided with an Indego® kit for the duration of the trial. This kit will include small (short), medium and large (tall) hardware components, all necessary padding options, and 2 hand held iPod touch operator controllers. Parker will provide “on call” engineering support.

Enrollment for PHIND_CVA01 will be on a rolling basis so that each site can enroll any number of subjects until the total subject number across sites reaches forty. Should a subject not complete all study sessions, an additional subject will be added to replace the person who did not complete the study. Data for persons who did not complete all sessions for the study will be analyzed separately.

Subjects may be enrolled from inpatient, day program, outpatient, post rehabilitation programs, or from home. Researchers will not attempt to have an equal representation among “programs” of when the subject was enrolled. However, the sponsor will attempt to have a mix of acute, sub acute and chronic conditions.

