EXPECTED TIMELINE TO COMPLETE 40 SUBJECTS ACROSS SIX SITES:

- 40 subjects for 2 week intervention = 80 weeks/6 sites = 13 weeks per site (3.25 months)
- Depending on site enrollment, total study duration should last roughly 8 months.

EFICACY ENDPOINTS**Primary Endpoint:**

- To show that the Indego® device is safe and potentially effective at providing gait training intervention for persons with hemiplegia due to CVA.

Supportive and Exploratory:

- Assess vital sign and skin
- Assess pain
- Assess impact of Indego training related to mobility measures.
- Assess changes in spasticity

SAFETY MEASURES

- Subjects must meet all inclusion criteria and possess none of the exclusion criteria
- Subjects must have medical clearance to participate prior to consenting process.
- Vital signs will be taken before and after each session

- Skin checks will take place before and after each session
- An Indego® certified PT will be present for all sessions.
- Sponsor will provide “on call” engineering support for the duration of the study.
- The six clinical sites chosen for the study are all experts in the field of neurological rehabilitation.
- All Subject Adverse Events and Serious Adverse Events will be documented, reported and followed to resolution.
- All device related adverse events to include device malfunctions pertaining to the device hardware, software or hand held controller interface will be documented, reported and followed to resolution.

STATISTICAL MEASURES

Forty subjects must complete all sessions for the study to be concluded. If any subject is unable to complete all sessions, their data will be analyzed separately and reported as a sub set to the main report.

A total sample size of 40 participants and over 200 Indego training sessions for this study will yield reasonable statistical power in determining the safety of the device and potential differences between pre- and post-test values, one-sample means tests, and Pearson correlation coefficients. When conducting matched pairs t-tests for pre- and post-test differences, 40 participants will yield a power of 0.87, with an alpha level of 0.05 and an effect size of 0.50, an effect size value that falls within the medium range according to Cohen (1998).

Cohen, Jacob. *Statistical Power Analysis for the Behavioral Sciences*. Hillsdale (NJ): Lawrence Erlbaum Associates, Inc.; 1998.

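### Power is claimed for safety, the primary objective, but no safety rate, limit, interval, test or analysis population is defined; the only power figure (0.87) belongs to the pre/post t-tests

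*Combined protocol and SAP*

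**What the plan says.** The Study Synopsis makes safety the primary objective: to demonstrate that the device "is safe to use as a gait training intervention for persons with hemiplegia due to CVA". It adds: "Results of this multi-site study to include 40 subjects will be submitted to the FDA as part of a 510K" application. The Primary Endpoint repeats this aim, adding potential effectiveness, and names no variable.

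On sample size, Statistical Measures says that 40 participants and "over 200 Indego training sessions for this study will yield reasonable statistical power in determining the safety of the device". The same sentence extends the claim to pre/post differences, one-sample means tests and Pearson correlations. The next sentence gives the only number: "When conducting matched pairs t-tests for pre- and post-test differences, 40 participants will yield a power of 0.87", at alpha 0.05 and effect size 0.50. That section ends by listing subject and device adverse events among the items to be described, without a population or denominator.

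On subjects who stop early, Study Design says that "an additional subject will be added to replace the person who did not complete the study" and that "Data for persons who did not complete all sessions for the study will be analyzed separately". Statistical Measures says that "their data will be analyzed separately and reported as a sub set to the main report". Safety Measures says, with no restriction to completers: "All Subject Adverse Events and Serious Adverse Events will be documented, reported and followed to resolution".

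**The concern.** Power is a property of a test of a stated variable against a stated reference value. For safety the plan supplies none of these, so the phrase has no calculation behind it. A reader of the submission could nevertheless take it that the safety result was sized.

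The second gap concerns who is counted. Withdrawal may itself follow an adverse event. If such a subject is replaced and analysed apart, the headline safety proportion can look better than the experience of everyone who used the device. The plan neither says that this will happen nor rules it out, because it names no safety population.

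**Working it through.** **Inputs from the plan.** n = 40 completers, alpha 0.05 (sidedness not stated) and effect size d = 0.50 (Statistical Measures); six sessions per subject, the first for consent, evaluation and fit (Study Design). **Assumed.** A 95% level for safety, and every safety limit, true rate and within-subject correlation below; the plan gives none.

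**1. The plan's own figure.** Paired t-test, df = 39, noncentrality d√n = 0.50 × √40 = 3.162. Power from the noncentral t distribution is 0.869 two-sided and 0.928 one-sided. The stated 0.87 is therefore right and corresponds to a two-sided test. It concerns a mean pre/post difference, not an event proportion.

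**2. Could a safety power be derived?** Not without a limit and a true rate. Suppose the aim were to exclude a per-subject risk at some limit, by an exact one-sided test at 0.05:

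| Assumed limit | Most events allowed in 40 | Power at true risk 1% / 2% / 5% |
|---|---|---|
| 5% | none suffices (0.95^40 = 0.129 > 0.05) | 0 / 0 / 0 |
| 10% | 0 | 0.67 / 0.45 / 0.13 |
| 15% | 2 | 0.99 / 0.95 / 0.68 |

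For the 10% row, power is (1 − p)^40; for example 0.99^40 = 0.67. The answer runs from zero to near certainty, depending on values that the plan does not state.

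**3. Precision from 40 subjects** (exact binomial, Clopper-Pearson).
- 0/40, one-sided upper limit: 1 − 0.05^(1/40) = 7.2%.
- 0/40, two-sided upper limit: 1 − 0.025^(1/40) = 8.8%.
- 1/40 = 2.5%: two-sided interval 0.06% to 13.2%.

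**4. Does counting sessions help?** Sessions 2 to 6 give 5 × 40 = 200; all six give 240. With no event in 200 independent sessions, the one-sided limit is 1 − 0.05^(1/200) = 1.5% per session. That holds only if sessions within a subject are independent. With within-subject correlation ρ, the effective number is 200/(1 + 4ρ). At ρ = 0.5 this is 66.7, and the limit is 4.4%. At ρ = 1 it is 40, and the limit is 7.2% again. Even under independence, 1 − (1 − 0.01487)^5 = 7.2% per subject. With no events, the session count changes the unit and not the evidence on risk per subject.

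**5. Who is counted (hypothetical).** One subject has an event, withdraws and is replaced. Completers: 0/40, two-sided upper limit 8.8%. All exposed: 1/41 = 2.4%, interval 0.06% to 12.9%.

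**The case against.** The strongest reply is that this is a single-group study that may properly report safety descriptively. The disputed sentence is loose and covers several analyses at once, the next one ties 0.87 expressly to matched pairs t-tests, and adverse events are already planned as descriptive. Much of this stands. A formal safety test or threshold is not obligatory, and 0.87 is neither wrong nor misattributed. But a descriptive safety analysis has no power, and the sentence claims it by name for the primary objective.

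Three stronger readings are tempting and are not supported:
- *Events in subjects who drop out would go unreported.* Safety Measures has all events reported, and non-completers' data appear as a subset. A reader would have to combine two sets of results; nothing is lost.
- *The main safety result is certain to be completers-only.* The separate-analysis sentences speak of data in general, and the adverse-event description names no population. Completers-only is the literal reading, not a stated rule.
- *Falls will be frequent, so their interval will be wider still.* The definition in Session Guidelines is broad, but the documents give no fall rate.

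**Conclusion.** The power claim for safety is wrong as written: the plan contains nothing from which such power could be calculated, and its one power figure concerns a different question. What 40 subjects can offer is precision. With no event of a given type, a per-subject risk of up to 7.2% (one-sided) or 8.8% (two-sided) remains compatible with the data. The smaller per-session limit depends on independence of sessions within a subject, which the plan does not discuss.

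The safety population is also unspecified, and no pooled summary of everyone exposed is planned. This second gap is modest, because the events remain reportable and the 0/40 against 1/41 contrast is only an illustration; no dropout rate is given. The precision figures rest on the assumed 95% level and exact binomial limits. This should be fixed, since it affects how the primary result is claimed and summarised in a regulatory submission.

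**What to change.** 1. **Statistical Measures, power sentences.** Take safety out of the power claim. State that 0.87 applies only to the matched pairs t-tests (two-sided alpha 0.05; the sponsor to confirm sidedness, which is inferred from the arithmetic), that no power is stated for any one-sample tests or correlations, and that safety is reported descriptively with its precision.

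2. **Study Design and Statistical Measures, non-completers.** Limit the separate analysis to the pre/post comparisons of mobility, strength and spasticity, and add:

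> The main safety summary (adverse events, falls, device events, skin, vital signs, pain) includes every subject who used the Indego at least once, whether or not they completed or were replaced; completers may be shown as a subset.

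3. **Statistical Measures, safety analysis.** Add:

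> The proportions of subjects with at least one adverse event, serious adverse event, device-related adverse event and fall are each reported with an exact two-sided 95% CI. With 40 exposed and no event the upper limit is 8.8%; it is recomputed for the actual number exposed. Any per-session rate allows for clustering within subject.

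**Cost.** Wording and a little more analysis of data already recorded at each session. There are no extra patients and no change to enrolment or replacement. The stated strength of the safety evidence becomes less favourable.
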